- In 2009, Galárraga used intraoperative botulinum toxin on 5 patients all younger than 6 months of age undergoing a primary cheiloplasty. The study showed the botulinum toxin injections to be safe without any complications observed. An EMG proven decrease in muscle activity around the repair site was also seen as predicted.
- Studies in adult patients have shown improved cosmetic outcomes for facial wounds when utilizing botulinum toxin. They have also established use of the toxin as safe in the face. Ziade et al. in 2013 showed injections of botulinum toxin type A within 72 hours postoperatively around facial wound repairs had better scar results at 1 year follow up as analyzed by 6 expert specialists. Wilson in 2006, showed utilization of botulinum toxin in revision facial scar surgery had 90 % of patients with a highly satisfactory outcome.

Objectives

Improve cheiloplasty outcomes with the use of intraoperative injection of botulinum toxin to clefted lip.

Study Design

- Randomized double blinded controlled trial of pediatric patients who require a primary unilateral cleft lip repair younger than 6 months of age. Utilization of botulinum toxin intraoperatively at targeted locations of the cleft lip. Surgeon, parents and expert panel of surgeons used at the completion study will all be blinded to which patients received the experimental injection.
- Control subjects will receive injections of normal saline at identical sites of the cleft lip as experimental subjects.
- 20 patients in each group will be enrolled.
- Patients will be evaluated preoperatively, postoperatively at 1 week, 1 month, 3 months, 6 months and 12 months of follow up.
- **Inclusion criteria:** Unilateral cleft lip with or without cleft palate, less than 6 months of age
- **Exclusion criteria:** Bilateral cleft lip, older than 6 months of age
- Primary endpoint: Blinded assessment of wound cosmesis by plastic surgeons and parents using scar assessment scale. At completion of follow up use of aesthetic grading criteria of videography images as described by Reddy et al. in 2008. These criteria include: Matching accuracy of white roll and vermillion border, scar appearance, Cupid's bow form, length of lip, nostril symmetry, alar dome form, and alar base position

Study Population

- Pediatric patients with complete unilateral cleft lip and palate less than 6 months of age undergoing cleft lip repair.

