Block randomization will be used for this study. The size of the blocks will not be fixed to ensure surgeons are truly blinded along with each arm of the study having the same number of patients. Therefore each group may have block sizes of 3, 5, 2, 6 and 4 to allow for a total of 20 patients. Both the ordering of blocks and their respective size will be blinded to eliminate any selection bias.

Drug Administration and Accountability

[name] MD, [name], MD and [name] will be responsible for botulinum toxin accountability. The toxin will be stored with the operating room pharmacy. As the study will be a randomized controlled trial, for those patients set to receive botulinum toxin, the medication will be requested from the OR pharmacy on the day of surgery. Prior to surgery it will be ensured the OR pharmacy has the toxin available. The toxin will be mixed as prescribed and 1 unit injections at 4 distinct sites will be used for a total of 4 units administered.

The pediatric plastic surgery research nurse will be responsible for notifying the operating room circulator whether that day's block of patients will be receiving the experimental versus the control injection.

Study patients will be attempted to be scheduled on the same OR days to maximize utilization of each botulinum toxin vial as they have a limited shelf life once mixed. Once the vial has been utilized it will be dispensed appropriately. The vials in the OR pharmacy will be stored in a standard cooled refrigerator as recommended by the manufacturer.

Possible Risks to Subjects

- Botulinum toxin safety has been well established. The FDA endorses that botulinum toxin use in a dermatologic fashion have no reported adverse side effects at the recommended doses. Studies which have utilized botulinum toxin in patients younger than 6 months of age have not reported significant adverse effects.
- Transient fatigue lasting no longer than 96 hours has been noted in a study by Pascual and Pascual in 2008 in one patient out of 74.
- The likelihood of risks are low and most studies have shown no side effects while few studies have noted transient fatigue in less than 5% of patients.
- Given that botulinum toxin takes 72 hours minimum to take effect there will be no change in the surgical procedure. Therefore there is no significant change in risk of the surgery itself.

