- Oleszek et al. in 2005 performed botulinum toxin injections for patients aged 6-18 months with congenital torticollis. 29.7 units of botulinum toxin were used on average for each patient. Only 2 patients had transient neck weakness with mild dysphagia that resolved without intervention. They showed that even at higher doses botulinum toxin was safe to use in the head and neck.
- Of note our study will only use a low dose of 4 units of botulinum toxin total and will approximately be 1 unit/kg dosing depending on the weight of our study patient. This dosage is less than most pediatric botulinum toxin injection studies to date and therefore should be a safe dosage.
- As noted above a large number of studies have shown botulinum toxin to be safe at both low and high doses at a variety of anatomic locations including the head and neck.

Safety Monitoring

The PI, co-investigator and mentor will review any reported adverse events monthly.

- Patients feeding capabilities, respiratory status, neuromuscular function and overall health will be evaluated on each scheduled follow up visit.

Statistics

- Using the Modified Vancouver Scar Scale we hypothesize the average score for controls to be 7 out of 11. For experimental patients we expect an average score of 10 out of 11. Given a 90% confidence interval and standard deviation of 2.5 the necessary sample size would be 15 subjects per group using a 2 sided test.
- Therefore 20 patients will be the goal group size for each arm of the study; botulinum toxin injection group versus control group.
- The study will be terminated if any subjects display significant adverse side effects that are potentially life threatening including feeding, cardiovascular or respiratory complications.
- Study subjects to be used will be all patients who will undergo a primary cleft lip repair that agree to participation in the study and subsequent randomization.

Ethics

- Prior to initiating the study University of Texas Health Science Center at Houston Institutional Review Board will need to grant approval for the study.
- Consent will be obtained in person at the time of the pre-operative visit in the University of Texas Pediatric Plastic Surgery clinic. This consent will be in addition to the consent obtained for the surgical procedure. The known risks and adverse effects of botulinum toxin will be fully disclosed to parents prior to obtaining consent for the study.

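### As written, each block receives a single injection, so about 10 blocks rather than 40 infants are randomised, while the sample size assumes individually randomised infants

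*Combined protocol and SAP*

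**What the plan says.** Three statements describe the allocation.

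- **Block Randomization:** block size varies, and "each group may have block sizes of 3, 5, 2, 6 and 4 to allow for a total of 20 patients". On concealment: "Both the ordering of blocks and their respective size will be blinded to eliminate any selection bias". No sequence of assignments within a block is described.
- **Drug Administration and Accountability:** the research nurse tells the circulator "whether that day's block of patients will be receiving the experimental versus the control injection". The same section says "Study patients will be attempted to be scheduled on the same OR days to maximize utilization of each botulinum toxin vial".
- **Statistics:** control mean 7 and experimental mean 10 out of 11, then "Given a 90% confidence interval and standard deviation of 2.5 the necessary sample size would be 15 subjects per group", two-sided, raised to a target of 20 per arm. There is no intraclass correlation, no design effect and no analysis by block.

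Some wording is at patient level. The pharmacy sentence reads "for those patients set to receive botulinum toxin, the medication will be requested from the OR pharmacy on the day of surgery", and the Statistics section refers to subjects agreeing to be randomised. On masking, Study Design says "Surgeon, parents and expert panel of surgeons used at the completion study will all be blinded to which patients received the experimental injection".

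**The concern.** In ordinary 1:1 permuted blocks, each block contains both arms. Here the blocks belong to a group, their sizes add up to one arm, and the only operating instruction assigns one injection to a day's block. Staff who follow it would give a whole block toxin or a whole block saline.

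The block is then the randomised unit. If infants in a block have correlated outcomes, for instance through a shared OR day, team or vial, a patient-level comparison rejects a true null too often, and the trial carries less information than its sample size implies. Treatment is also tied to OR day.

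Blinding is affected too. Anyone in the operating room who learns one infant's arm knows the arm of every other infant in that day's block. That works against the stated purpose of varying the block size, which is to keep surgeons blinded.

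**Working it through.** **1. The plan's own figure.** Inputs from the Statistics section: difference 10 − 7 = 3, SD 2.5, two-sided.

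n = 2(SD/difference)² (z₁₋α/₂ + z_power)² = 2(2.5/3)² (1.960 + 1.282)² = 14.6, so 15 per group.

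This matches if the 90% is power and alpha is 0.05. If the 90% is taken literally as the confidence level (alpha 0.10), 15 per group gives about 95% power. Either way the formula treats infants as independent. By noncentral t, individually randomised infants give:

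- 15 per arm: 88.7% power at alpha 0.05, 94.1% at 0.10
- 20 per arm: 95.9% and 98.1%

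**2. Units under whole-block allocation.** 3 + 5 + 2 + 6 + 4 = 20, so 5 blocks per arm and 10 in all. Degrees of freedom fall from 40 − 2 = 38 to 10 − 2 = 8. The possible orders of 5 toxin and 5 saline blocks number C(10,5) = 252.

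**3. Design effect.** Σm²/Σm = (9 + 25 + 4 + 36 + 16)/20 = 90/20 = 4.5, so DE = 1 + 3.5 × ICC and effective n per arm = 20/DE. This falls below 15 once ICC exceeds (20/15 − 1)/3.5 = 0.095.

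**4. Error and power.** The ICC is an assumption, shown from 0 to 0.20. True error and unweighted block-mean power come from simulation (200,000 trials, 5 blocks per arm of the listed sizes, SD 2.5, difference 0 or 3). Size-weighted power is noncentral t on 8 df with noncentrality 3/(2.5√(2·DE/20)). Paired entries are for nominal 5% / 10%.

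| ICC | DE | Effective n per arm | True error, patient-level t-test | Power, unweighted block means | Power, size-weighted block means |
|---|---|---|---|---|---|
| 0 | 1.000 | 20.0 | 5.0% / 10.0% | 87% / 94% | 91% / 96% |
| 0.05 | 1.175 | 17.0 | 7.1% / 13.1% | 83% / 92% | 86% / 94% |
| 0.10 | 1.350 | 14.8 | 9.2% / 15.8% | 79% / 89% | 82% / 91% |
| 0.20 | 1.700 | 11.8 | 13.7% / 21.3% | 72% / 84% | 72% / 84% |

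Optimal weights with a known ICC add about one point at most (73.4% and 85.2% at ICC 0.20). From ICC 0.05 upward, a block-level test on 20 per arm has no more power than 15 per arm individually randomised.

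**5. The other reading.** The listed sizes could be what each arm contributes to a mixed block. Total sizes would then be 6, 10, 4, 12 and 8, which sum to 40 and split exactly 1:1. None of the loss above would apply. However, a mixed block cannot be described as receiving one injection or the other, which is what the nurse's instruction does. If the listed sizes are total block sizes instead, 3 and 5 cannot be split 1:1.

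**The case against.** The best case against is that this is loose wording, not a cluster design. The sizes are only examples, the mixed-block reading is arithmetically clean, and the pharmacy and consent wording is about patients. The contrary evidence on the nurse's message is a single logistics sentence, in which a block may just mean the day's list.

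Accrual points the same way. A 24-month study with at least 12 months' follow-up leaves about 12 months to enrol 40 infants, or 40/12 = 3.3 a month. A block of 6 would take nearly two months to fill (6/3.3 = 1.8), so a listed block can hardly always be one OR day. If the shared unit is really the OR day, clusters are probably smaller and more numerous, and neither the 8 degrees of freedom nor the factor 3.5 would hold.

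The size of the harm rests on an ICC the documents do not give, and at ICC 0 there is no inflation. Going from 15 to 20 per arm absorbs the loss of effective n up to an ICC of about 0.095. No analysis is named beyond a two-sided test, so the patient-level t-test is an assumption of this review. On blinding, controls get saline at the same sites, the protocol says toxin takes at least 72 hours to act, and the panel rates coded videos.

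Most of this stands as a limit on size. It does not remove the defect: whatever the number of clusters, the instruction gives infants in a day's block one common arm, and nothing in the text tells staff to do otherwise.

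**Conclusion.** The concern holds. Followed as written, the plan allocates whole blocks, about 10 on the illustrative sizes, while the sample size is for independently randomised infants. The authors may have intended individual randomisation, but the text must be corrected on either reading.

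The size is conditional. It assumes 5 blocks per arm of the listed sizes, a patient-level t-test as the default analysis, and an ICC that the documents do not supply. The effect is nil on error at ICC 0, moderate at 0.05 and serious by 0.20.

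The blinding weakness does not depend on the ICC, but its extent is unknown because block order and size are concealed. A leak in the operating room does not by itself reach the expert panel.

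**What to change.** Randomise infants individually 1:1 in concealed permuted blocks of randomly varying even size (for example 2, 4 and 6), each half toxin and half saline, summing to 20 and 20. Replace the nurse's day-level message with each infant's own assignment, so that one OR day can contain both arms. Same-day scheduling to share a vial can stay.

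If whole-block allocation is deliberate, state it, make the block the unit of analysis, and restate the power with an explicit ICC range. In either case, state alpha and power separately.

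The cost is a new randomisation list and a short amendment, with no extra patients or staff. A toxin vial may be opened on more OR days; the documents do not give enough to say how many. The change has to be made before the list is used, because allocation cannot be repaired after infants have been treated.

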- All patients who will be planned for a primary cleft lip repair will be offered to be enrolled in the study. Parents may choose to decline and undergo repair without enrollment in the study.
- Patients will be recruited as they would present otherwise to the University of Texas Pediatric Plastic Surgery Clinic to be evaluated for repair of cleft lip.

Study Procedures

- Patient will receive intraoperative botulinum toxin injections in the upper labial musculature prior to the operative repair being started.
- 4 injection sites will be used two superior and inferiorly in the cleft lip, 1 unit of botulinum toxin per injection site to be used. This is considered low dose in the pediatric population. Depending on the patient's weight it will be approximately 1 unit/kg.
- This dosing was chosen as it has been proven safe without any complications in prior pediatric botulinum toxin studies.
- This dosage has also been shown to adequately elicit muscle paresis in the head and neck.
- Patients will have videography performed preoperatively as well at scheduled post-operative visits.
- Parents will complete a Modified Vancouver Scar Scale at selective post-operative visits
- The Vancouver scar scale is a widely used validated scar scale for adults, however given our study it was modified appropriately for pediatric populations. There is no validated scar scale for pediatric patients.
- At the completion of the 1 year follow up period, videography will be sent to an expert panel of select plastic surgeons that will also use the Modified Vancouver Scar Scale to assess scar outcomes in both the control and experimental groups. This panel will be blinded to which patients received botulinum toxin and which received the control injection.
- Videography at the completion of the study will also be assessed for the following measures: Matching accuracy of white roll and vermillion border, scar appearance, Cupid's bow form, length of lip, nostril symmetry, alar dome form, and alar base position. Study personnel will be blinded to which patients received the experimental injection.
- No invasive procedures or postoperative monitoring will be employed unless deemed medically necessary.

Block Randomization

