- Consent will also be required to be obtained for videography that will be used pre/post operatively to evaluate cosmesis of the repair.

Data handling and record keeping

- Operative reports will be securely located in the Care4 EMR of Memorial Hermann Hospital which is the hospital affiliated with the University of Texas Medical School at Houston where the cleft lip repairs will occur.
- All data will be securely located on a LOK IT secure flash drive as approved by the University of Texas Medical School at Houston. LOK IT secure flash drive is password coded and identified as a suitable way to store patient sensitive data.
- Videography will also be kept on this secure LOK IT flash drive to ensure confidentiality.
- A computer supplied and maintained by the University of Texas Medical School at Houston that is in the Otolaryngology resident work room will be the main computer used when accessing and analyzing data/images. The computer is password protected and is approved for use by the medical school for data collection use.
- Images of the patient will only include the face to assess the outcomes of the repair. All images taken at planned post-operative visits will be taken with the same camera and calibration settings.
- Data and images will be coded by a discrete number that will be used to identify an individual patient and their repair. No patient identifiers will be linked to the videos

Quality control and assurance

- Videography camera will be operated by a select number of users that have been taught the appropriate amount of training to operate it appropriately.
- Camera will be calibrated prior to each session to ensure consistent videography.
- A modified Vancouver Scar Scale will be given to parents at post-operative visits.
- Botulinum toxin will be prepared in the same manner for each patient.

Publication Plan

- Plan to submit abstract and manuscript to reputable conferences and otolaryngology journals at the completion of the study.

ATTACHMENTS

1. Study Schedule
2. Consent Document
3. Modified Vancouver Scar Scale
4. Aesthetic grading criteria table

REFERENCES

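### The day-of-surgery workflow brings the treatment arm into the operating room, and nothing written keeps it from the surgeon

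*Combined protocol and SAP*

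**What the plan says.** Study Design calls the trial double blinded and states: "Surgeon, parents and expert panel of surgeons used at the completion study will all be blinded to which patients received the experimental injection". It matches the control injection by site: "Control subjects will receive injections of normal saline at identical sites of the cleft lip as experimental subjects".

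Block Randomization gives surgeon blinding as one reason for varying the block size, and conceals the order and size of blocks.

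Drug Administration and Accountability sets out the day itself. On supply: "for those patients set to receive botulinum toxin, the medication will be requested from the OR pharmacy on the day of surgery". On communication, the "research nurse will be responsible for notifying the operating room circulator". The content of this notice is the arm for the day, that is, whether the "block of patients will be receiving the experimental versus the control injection".

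Study Procedures places the toxin injections "in the upper labial musculature prior to the operative repair being started". The one quality-control statement on preparation is "Botulinum toxin will be prepared in the same manner for each patient".

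**The concern.** A blinding promise is only as good as the handling of the product on the day. Here the written steps create two signals of the arm in or near the operating room: a drug request tied to one arm, and an explicit notice to a member of the operating room staff. No step is written to stop either signal reaching the surgeon.

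The stake is the conduct of the repair. The surgeon's work follows the injection and helps determine the scar that is later rated. If the surgeon knew the arm, the repair or the care around it could differ between arms. Blinded raters could not undo that, because they would be scoring a real difference that the toxin had not caused.

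**Working it through.** No statistical calculation applies. The check sets the promise beside each step that could deliver it.

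1. **Who must not know.** Study Design names the surgeon, the parents and the expert panel.

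2. **What is ordered.** The request to the OR pharmacy is described for toxin patients. No section describes a request, a source or a preparer for saline. With 20 infants per arm, a request is described for 20 of the 40 and none for the other 40 − 20 = 20. If practice follows the text literally, the presence or absence of a request marks the arm.

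3. **Who is told.** The circulator is told the injection type for the day's block, whichever arm it is. That covers 40 of 40 infants.

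4. **How the product is masked.** The toxin is to be mixed as prescribed. No section says who fills the syringes, who injects, whether toxin and saline syringes look alike, or how they are labelled. The quality-control statement is about consistency and covers toxin only. By their titles, the four listed attachments (schedule, consent, scar scale, grading criteria) do not concern preparation.

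5. **When knowledge would arrive.** The injection precedes the repair, so knowledge of the arm at that point would precede the whole operation.

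6. **What each existing safeguard covers.**
   - Saline at identical sites matches the site and the act of injecting, not the order or the syringe.
   - Varying block sizes and concealing their order protect the allocation sequence from being guessed. They do not conceal the product in the room.
   - The blinding statements for the panel and the video assessment (Study Procedures), and number-coded videos (Data handling and record keeping), protect outcome assessment.

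   None of these governs the request or the notice on the day of surgery.

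7. **A related ambiguity.** The listed block sizes add to 3 + 5 + 2 + 6 + 4 = 20, the size of one arm, and the notice speaks of one injection type for the day's block. Both suggest single-arm blocks, but the text does not say so. If blocks are single-arm by day, identifying one infant's arm would reveal that day's group.

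**The case against.** The best defence is that someone must know the arm in order to supply the right product. The protocol sends that knowledge from nurse to circulator, and nowhere gives it to the surgeon. On this reading the notice is part of the blinding, and only operational detail is missing. Part of this stands: an informed circulator is compatible with a blinded surgeon, so a reader who infers that the surgeon is unblinded goes beyond the text. But the separation that would make the arrangement safe is not written anywhere.

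A reader might also infer that nothing is requested from the pharmacy for controls. The documents are silent on this; they do not exclude a saline order. The point is therefore what is described, not what is known to happen.

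The risk section says that toxin takes at least 72 hours to act, so the surgical procedure will not change. That does weaken any argument that the drug alters the operation through its pharmacology. It is a statement about surgical risk, however, and does not conceal the arm.

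Two further inferences are tempting and unsupported. The first is leakage from the nurse to the parents, prompted by "Parents will complete a Modified Vancouver Scar Scale at selective post-operative visits". No section places the research nurse at those visits, and parents are stated to be blinded. The second is a count or percentage of infants exposed by one leak. That would need the number of infants per OR day, which is not given, and a settled reading of the block scheme.

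**Conclusion.** The concern holds as a gap in the written protection of surgeon blinding, and it should be fixed. It is more than missing detail, because the workflow as stated carries the arm to operating room staff before the repair. Its extent is the workflow for all 40 infants, with the described toxin request applying to 20 of them. Its effect on the result cannot be sized: the documents support neither a probability of a leak nor a magnitude of bias. The panel and video assessors are not directly exposed through this route. The conclusion assumes that the public text describes the whole procedure. If masked preparation already takes place, what remains is to write it down.

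**What to change.** In Drug Administration and Accountability, replace the toxin request and the notice to the circulator with wording such as:

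> *A study injection is ordered for every enrolled infant. The OR pharmacy prepares it from the allocation list as identical, equal-volume syringes of toxin or normal saline, labelled only with the study number. The circulator and the surgical team are not told the allocation. Anyone who knows the allocation does not operate, conduct follow-up visits or score outcomes. The pharmacy-held list remains available for emergency code-break.*

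In Block Randomization, state whether each block contains one arm or both. The change above does not remove the risk that, with single-arm day blocks, one identified infant reveals the group. Moving to mixed-arm blocks would be a separate decision and might use more vials.

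The cost is revised protocol and order wording, 20 saline preparations (one per control infant), and pharmacy time that the documents do not quantify. The pharmacy, which already stores the toxin, would also hold the allocation list. If any of those accountable for the toxin also operate, follow up or score, that task must pass to someone else; names are removed, so this cannot be checked. Allocation and same-day scheduling are unchanged, so no extra toxin vials are needed. No dose, injection site or clinical rule changes.

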- Also of note this study will be using botulinum toxin doses lower than most studies already completed, therefore the risk should be less as the risk of botulinum toxin is dose dependent.
- Two prior cleft lip studies utilizing botulinum toxin reported good outcomes with no complications or feeding difficulties.

Rare reported adult adverse side effects of botulinum toxin include: Difficulty swallowing, breathing, speaking, feeding, diffuse muscle weakness, double vision, voice changes, allergic reaction and bladder dysfunction. However, no documented adverse effects have been noted when used at dermatologic doses on the face.

Safety

- Two studies on cleft lip patients younger than 6 months of age utilizing botulinum toxin have been completed without any complications and shown the toxin to be safe in this population.

Prior cleft specific studies

- Tollefson et al. in 2006 with 3 patients and Galarraga in 2009 with 5 patients used botulinum toxin injections in the cleft lip without any reported complications.

Prior pediatric botulinum toxin studies

- Botulinum toxin injections are also used for a large variety of pediatric conditions safely including ophthalmologic, gastrointestinal and neurological.
- Messner et al. in 2011 used 7 botulinum toxin injections in 3 patients younger than 6 months of age with for cricopharyngeal achalasia. Injections were done in the cricopharyngeus muscle with successful treatment allowing patients to eat by mouth as a result. No complications were encountered with an average follow up of 22 months, 3.3units/kg of botulinum toxin were used.
- Pascual and Pascual in 2008, reviewed botulinum toxin injection safety in patients younger than 2 years old. 74 patients received botulinum toxin injections with 28 younger than 1 year of age. Only 1 patient was noted to develop transient fatigue that lasted less than 4 days without intervention. All other patients did well with no significant adverse effects. On average 6.55 units/kg for patients less than 1 year of age and 8.4 units/kg in patients 1-2 years old were used. They deemed botulinum toxin injections safe at the appropriate dosage.
- Chhina et al. in 2013 showed higher dosages of botulinum toxin were safe in patients less than 2 years of age. Injections were done in the feet on patients with clubfeet. 239 patients and 361 feet were injected with 10 units/kg. No complications were noted in any patient and again deemed botulinum toxin injections safe.

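### The protocol does not actively ask about adverse events since surgery or the last visit, so short-lived effects may be under-recorded

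*Combined protocol and SAP*

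**What the plan says.** The Safety Monitoring section has two elements. The first is assessment at visits: "Patients feeding capabilities, respiratory status, neuromuscular function and overall health will be evaluated on each scheduled follow up visit". The second is a review of reports: "The PI, co-investigator and mentor will review any reported adverse events monthly". Study Design gives the schedule: "Patients will be evaluated preoperatively, postoperatively at 1 week, 1 month, 3 months, 6 months and 12 months of follow up".

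The protocol does not say who reports events between visits, by what route, over what recall period or in answer to which questions. Study Procedures adds "No invasive procedures or postoperative monitoring will be employed unless deemed medically necessary"; the word for invasive may or may not be meant to qualify monitoring as well.

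On timing, Possible Risks to Subjects states "Transient fatigue lasting no longer than 96 hours has been noted in a study", in one child of 74, and says that "botulinum toxin takes 72 hours minimum to take effect". The same section puts fatigue at under 5% of patients in the few studies that saw it. Under the prior paediatric studies, the Safety section reports from a torticollis series aged 6 to 18 months: "Only 2 patients had transient neck weakness with mild dysphagia that resolved without intervention". Possible Risks names fatigue as the only effect seen in paediatric studies and places swallowing trouble in an adult list: "Rare reported adult adverse side effects of botulinum toxin include: Difficulty swallowing".

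**The concern.** Evaluating an infant's status at a visit records what is present that day. An effect that came and went beforehand is recorded only if someone asks about the interval or a parent volunteers it. The monthly review handles reports once they exist; it does not generate them. Since every paediatric effect the protocol cites was transient, these are the events that this method is least suited to record.

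At stake is how a finding of few or no adverse effects in about 20 treated infants can be read. If capture is incomplete and of unknown extent, a low count mixes a low event rate with missed events, and the trial would have no data to separate them.

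The two safety texts also disagree. Someone drafting adverse event questions or risk wording from Possible Risks alone would see fatigue as the only effect reported in children, although the Safety section reports neck weakness with mild dysphagia in young children.

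**Working it through.** The plan gives no calculation of event detection, so there is no figure of its own to reproduce here. Its two descriptions of the fatigue case agree: at most 96 h in Possible Risks, under 4 days in Safety.

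**Inputs from the protocol**
- First post-operative visit: 1 week = 168 h. Next visit: 1 month, taken as day 30.
- Earliest toxin effect: 72 h (day 3).
- Longest duration stated for a cited paediatric event: 96 h (4 days), in one child.
- Event rates: 1/74 = 1.35% (the one count with a denominator) and 5% (the ceiling given for fatigue).
- Toxin arm: 20 infants.

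**Timing**
- Onset 72 h, duration 96 h: 72 + 96 = 168 h, so it ends at the first visit. A shorter episode from the same onset is over by then.
- Onset 96 h, duration 96 h: 96 + 96 = 192 h, so it is still present at the first visit.
- Onset just after day 7, duration 96 h: over by about day 11, within the gap of 30 − 7 = 23 days before the next visit.

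**Share of episodes present at a visit.** The onset distribution is an assumption, because the documents give no onset time for any cited event. Capture c = (onset days from which an episode is present on day 7 or day 30) / (all onset days).

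| Assumed onset, uniform over | c, 96 h episodes | c, 48 h episodes |
|---|---|---|
| days 3–7 | 4/4 = 100% | 2/4 = 50% |
| days 3–10 | 4/7 = 57% | 2/7 = 29% |
| days 3–14 | 4/11 = 36% | 2/11 = 18% |
| days 3–30 | (4+4)/27 = 30% | (2+2)/27 = 15% |

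**Chance of recording at least one event in 20 toxin infants** = 1 − (1 − p·c)^20, where p is the true rate and anything not present at a visit is assumed lost.

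| c | p = 5% | p = 1/74 |
|---|---|---|
| 100% | 1 − 0.95^20 = 64% | 1 − (73/74)^20 = 24% |
| 50% | 40% | 13% |
| 30% (8/27) | 26% | 8% |
| 15% (4/27) | 14% | 4% |

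**Zero events with full capture**
- At 1/74: (73/74)^20 = 76%.
- At 5%: 0.95^20 = 36%.
- One-sided 95% upper limit for 0/20: 1 − 0.05^(1/20) = 13.9%. This limit presumes that every event is captured.

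**The case against.** The strongest reply has four parts.

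**Other routes exist.** A reader might infer that safety is looked at only at visits. The text does not support that: the monthly review allows for reports made at other times. Nor does anything stop a clinician from asking about the interval when evaluating feeding and general health. This stands, and it removes any claim that reporting is confined to visits. The reporting route and recall period remain undefined.

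**The timing is less damaging than it looks.** A reader might infer that most events would be over before the first visit. That cannot be derived. Of the three cited paediatric cases, only the fatigue case has a duration and none has an onset time. The 72 h figure is a minimum, given to explain why the operation itself is unaffected. With onset on days 3 to 7, every 96 h episode is present at or reaches the 1-week visit. This also stands.

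**Small numbers dominate.** A reader might infer that 0/20 would reflect the timing of examinations rather than an absence of events. At 1/74, zero is 76% likely even with perfect capture, so the inference fails. Incomplete capture adds to the problem; it is not the sole cause.

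**The cited dysphagia is remote, and feeding is already assessed.** Those children were aged 6 to 18 months and received 29.7 units on average, against 4 units here, and Safety Monitoring already names feeding, respiratory status and neuromuscular function. This is fair. It limits the mismatch between sections to a wording point that still needs reconciling.

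Two limits also apply. The Study Schedule and Consent Document are listed as attachments but were not in the text reviewed, and might describe further contacts. The plan states no comparison of safety between arms, so no planned analysis is biased.

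**Conclusion.** The point holds in limited form. The protocol text evaluates status at visits and reviews what is reported, but does not actively solicit events since surgery or the last visit. Brief events may therefore be under-counted.

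The size is uncertain. At a true 5% rate with 96 h episodes, the chance of recording at least one event in 20 treated infants runs from 64% to 26% across the onset assumptions shown. Episodes of 48 h would give 40% to 14%. These are illustrations, not bounds. They rest on assumed onset distributions, on a rate at the protocol's stated ceiling, and on nothing being recalled at visits; any recall or spontaneous report raises capture.

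The point should not be extended to the termination condition in the Statistics section. That condition concerns potentially life-threatening effects, whereas the cited dysphagia and fatigue resolved without intervention. This is a low-cost improvement to data collection, not a flaw in the cosmetic comparison.

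**What to change.** In Safety Monitoring, add that at every scheduled visit parents in both arms, with allocation still blinded, answer the same fixed questions about events since surgery or since the last visit. The questions should cover fatigue, feeding and swallowing, breathing, and neck or general weakness, with start and stop dates. State how parents report events between visits. The form can accompany the parents' scar form; because Study Procedures has the scar form completed only at selected visits, say explicitly that the safety questions apply at all of them. A diary card from surgery to the 1-month visit is optional.

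In Statistics, add a table of the number of infants with any such event by arm, with an exact upper confidence limit for any zero count (13.9%, one-sided 95%, for 0/20).

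Reconcile Possible Risks to Subjects with the Safety section, so that both give the same account of dysphagia and neck weakness reported in young children. Check the Study Schedule and Consent Document for consistency with the result.

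The cost is one short form and no added visit. The downside is a few more minor events recorded in both arms.
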